**A Comparative Study of Tubeless Percutaneous Nephrolithotomy With or Without Reverse Ureteral Catheter Insertion**

NCT number: NCT05574517  
Version number: V2.0  
Release date: October 8, 2022

1. Title: A comparative study of tubeless percutaneous nephrolithotomy with or without reverse ureteral catheter insertion.
2. Trial registration: Clinical Trial Registry (<https://www.clinicaltrials.gov>).
3. Version number and date: Version Number: V1.0 Version date: September 23, 2022.
4. Funding: Key Clinical Research Project of University of South China (No. USCKF201902K01).
5. Investigator and responsibilities: [name], deputy chief physician (study leader) : trial design, surgical implementation, protocol management, and process guidance; Research group postgraduate: data collection and analysis, article writing and publication.
6. Research background and principle: PCNL is the first-line treatment for renal calculi and upper ureteral calculi. With the development of minimally invasive urological endoscopic technology and the improvement of patients' medical requirements, it has become a consensus that PCNL surgery will develop in the direction of less trauma, more concise operation and more reasonable innovation. The emergence of tubeless PCNL (without indwelling nephrostomy tube) has been proved to be safe and effective in reducing postoperative discomfort, shortening hospitalization time and reducing hospitalization costs, so it has been paid more and more attention by clinical medical workers. Traditional tubeless PCNL usually requires placing the patient in the lithotomy position and retrograde insertion of the ureteral catheter under transurethral ureteroscopy, which is theoretically considered to be used to establish "artificial hydronephrosis" guided puncture and to prevent stones from falling into the ureter to form ureteral stone street. However, a large number of practices have found that the reverse insertion of ureteral catheter can cause many ureteral-related surgical complications. And for those who have had spinal injury, spinal deformity or large joint stiffness of the body of the patient, often can not swing the lithotomy position. At this time, without reverse insertion of ureteral catheter can show its unique advantages: simplify the operation steps, shorten the operation time, reduce the repeated operation of the ureter and thus

reduce the risk of long-term ureteral stenosis. However, there are few reports on tubeless PCNL without reverse ureteral catheter insertion. With the continuous update of ultrasound equipment and the continuous progress of physician puncture technology, ultrasound-guided percutaneous renal puncture is less and less dependent on retrograde pyelography or artificial hydronephrosis. Therefore, we believe that for patients with certain hydronephrosis and little stone burden, it is theoretically feasible to perform tubeless PCNL without reverse insertion of the ureteral catheter.

7. Objective: The purpose of this study is to explore the safety and clinical efficacy of this new surgical method in the treatment of upper urinary calculi by combining the application of non-inverse insertion technique in the operation of tubeless PCNL, and to explore the applications of this new surgical method.

8. Experimental design: A two-arm parallel trial design was carried out. The participants who underwent tubeless PCNL without reverse insertion of a ureteral catheter were selected as the experimental group, and the participants who underwent traditional tubeless PCNL with reverse insertion of a ureteral catheter were selected as the control group.

9. Site: This was a single-center study conducted at the First Affiliated Hospital of the University of South China.

10. Inclusion and exclusion criteria: Inclusion Criteria: 1. Participants who met the the applications of PCNL surgery in the 2019 Chinese Guidelines for the Diagnosis and Treatment of Urological Diseases; 2. Participants who agree to undergo tubeless PCNL; 3. The participants' maximum diameter of the stone should be less than 3.5cm. Exclusion Criteria: 1. Confirmation by computerized tomography (CT) images and blood biochemical indicators of infectious stones or complex staghorn stones; 2. Obvious surgical contraindications, such as severe heart and lung insufficiency, abnormal coagulatory function; 3. Previous PCNL or nephrolithotomy, presence of an indwelling ureteral stent or nephrostomy tube before surgery; 4. Renal trauma or congenital malformation of the urinary system. If the following variations occurred during the operation: puncture difficulties in the

[figure not shown]
lithotomy position and inverse insertion of ureteral catheter-guided puncture, a finding that pyonephrosis demanded the treatment of nephrostomy, channel bleeding that was required to maintain a nephrostomy tube, larger residual calculi that needed a nephrostomy tube for a secondary surgery, or a ureteral stone street that necessitated ureteroscopic lithotomy by changing to the lithotomy position; Or incomplete postoperative clinical data will be recorded by the study recruitment flow chart, but not included in the final data analysis.

11. Intervention measures: a. According to the randomization, the same associate chief urologist performed tubeless PCNL without reverse ureteral catheter or traditional reverse ureteral catheter; B. During the perioperative period, participants were given comprehensive blood biochemical examination and imaging evaluation, and antibiotics (second-generation cephalosporins or penicillins) were prophylactic. Participants with hypertension, diabetes and other comorbidities were given relevant drugs to control the tolerable level of surgery. C. Implementation process of tubeless PCNL without reverse insertion: After detaining urethral catheter for patients with tracheal intubation general anesthesia, to take a prone position, suffer renal biopsy under ultrasound guided look straight into the target under the calyces, syringe after water injection and suction is smooth, the guide wire guided by micro fascia dilator (Fr16 or Fr18) continuous build percutaneous renal channel expansion, step by step with holmium laser remove all break "can see the stone", A 6Fr double J tube was placed antegrade under the guidance of the guide wire, and no stone residue was detected. No active bleeding was observed in the channel during the withdrawal of the lens. The implementation process of traditional reverse insertion of tubeless PCNL was as follows: the participants were intubated for general anesthesia. First, the ureteral catheter was inserted under transurethral ureteroscopy in the lithotomy position and fixed on the catheter. The process of establishing percutaneous renal channel under ultrasound guidance and stone removal was the same as that of tubeless PCNL without the use of a retro-inserted ureteral catheter. Double J tubes were placed antegrade under the guidance of guide wire, and the

skin incision was sutured and closed after no residual "visible stones" and no active bleeding under endoscopic observation.

12. Outcome measures: The primary clinical end point was the incidence of postoperative complications (including postoperative fever, bleeding, pain, and changes in renal function; Ureterostone street was formed after operation. Air - fluid chest after operation); The secondary clinical end points were operation time, hospital stay, hospital cost and stone clearance rate.

13. Recruitment flow chart:

14. Sample size: Combined with the number of outpatient calculi patients and the number of PCNL surgeries in our department of Urology each year, we planned to initially include 200 patients with renal and/or upper ureteral calculi who underwent tubular PCNL surgery in our hospital from October 2022 to December 2024, and randomly assigned at 1:1.

15. Participants: Patients with upper urinary stones attending the Urology Clinic of the First Affiliated Hospital of the University of South China were recruited.

16. Allocation sequence generation, allocation hiding, implementation methods: Computer random number generator was used. Participants with odd numbers were assigned to experimental group, where they underwent tubeless PCNL without

reverse insertion of a ureteral cathete. Participants with even numbers were assigned to control group and underwent tubeless PCNL with reverse insertion of a ureteral cathete. This process takes place in the operating room.

17. Blinding: In a single-blind approach, patients are told to participate in a clinical trial but are not informed about the specific intervention, while the person administering the intervention is clearly informed.

18. Data collection: The measured data of all the required: 1. The demographic data, stone characteristics and preoperative baseline data, including the proportion of gender, age, body mass index (BMI) and basic diseases distribution, location, stones, stone maximum cross-sectional area, the longest diameter antler shape proportion and pelvic effusion width, partial side and puncture operation, etc. 2. Data of the main end points included: Postoperative fever and inflammation (temperature, preoperative blood leukocyte count difference after operation, neutrophils ratio difference, post-operative sepsis), postoperative bleeding (preoperative differential postoperative hemoglobin and hematocrit value and blood in the urine, subcapsular renal week or hematoma after operation, postoperative DSA guided by selective renal artery embolization bleeding), postoperative pain, postoperative analgesia drug demand, Mainly non-steroidal anti-inflammatory analgesic drugs), renal function changes (preoperative and postoperative serum creatinine difference), ureteral stone street formation rate and the incidence of gas and fluid chest (postoperative CT showed the presence of gas and fluid accumulation in the chest); Secondary end points included operation duration, length of hospital stay, hospitalization cost, and stone clearance rate. 3. Follow-up was conducted for 1 month after discharge, including: high fever, obvious pain and hematuria after discharge; Whether there is readmission; Whether to remove the double J tube as scheduled.

19. Statistical analysis plan: SPSS26.0 statistical software was used for analysis. Measurement data were expressed as mean  $\pm$  standard deviation ( $X \pm S$ ) and t-test was used. Enumeration data were expressed as frequency and percentage by  $X^2$  or Fisher exact test. Rank sum test was used for rank data.  $P < 0.05$  was considered

statistically significant.

20. Ethical approval: This trial was a human life science and medical study and was approved by the Medical Ethics Committee of the First Affiliated Hospital of the University of South China (No. : 2022110924001).

21. Informed consent: All participants enrolled in the study signed a surgical consent and a clinical trial informed consent to collect and use the medical behavior information and biological samples for the study.

22. Confidentiality measures: The identifiable information of the subjects is replaced by irrelevant character sequences to ensure that the relevant personal information of the subjects will not be disclosed in any form.

23. Declaration of Interest: There is no conflict of interest between the investigator and the organization.

24. Data Acquisition: When proper editing or review requirements are met, the study data may be obtained from the study manager after the study is completed.

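### No eligibility criterion requires suitability for both operations, although the protocol names patients who often cannot take the position in which the control operation starts

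*Protocol*

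**What the plan says.** Protocol section 6 (background) states that patients with an injured or deformed spine or with stiff large joints "often can not swing the lithotomy position". The next sentence introduces the advantages of omitting the retrograde catheter in that situation.

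Section 11 describes the two operations. In the control arm, "First, the ureteral catheter was inserted under transurethral ureteroscopy in the lithotomy position and fixed on the catheter". In the experimental arm the sequence is "After detaining urethral catheter for patients with tracheal intubation general anesthesia, to take a prone position"; no lithotomy step is described.

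Section 10 has three inclusion criteria: guideline indications for PCNL, agreement ("Participants who agree to undergo tubeless PCNL"), and a stone diameter limit of 3.5 cm. It has four exclusion criteria. The nearest to this issue is "Obvious surgical contraindications, such as severe heart and lung insufficiency, abnormal coagulatory function". Another excludes congenital malformation, but only of the urinary system. Section 10 also lists intraoperative events that are recorded in the flow chart and left out of the analysis. One of them is a stone street needing "ureteroscopic lithotomy by changing to the lithotomy position".

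Sections 14 and 16 plan 200 patients, assigned 1:1 by odd or even random number, in the operating room.

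**The concern.** A randomised comparison of two operations needs every participant to be a candidate for both before allocation. Here the protocol itself identifies a type of patient who often cannot be placed in the position that one arm requires, and sets no criterion that clearly keeps such patients out of the draw.

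The difficulty is asymmetric. A patient who can lie prone but cannot take lithotomy can receive the experimental operation as described if allocated to it, but not the control operation as described. Any non-adherence at the start of surgery for this reason therefore arises only in the control arm. These patients may also differ from the rest in complication risk, and complications are the primary end point. If they leave the control arm while their counterparts stay in the experimental arm, randomisation no longer balances the groups.

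**Working it through.** **1. Criteria set against the two procedures**

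| Protocol item | Does it address positioning or suitability for both arms? |
|---|---|
| Inclusion 1: guideline indications for PCNL | Not stated; the guideline is not reproduced |
| Inclusion 2: agreement to tubeless PCNL | No |
| Inclusion 3: stone under 3.5 cm | No |
| Exclusion 1: infectious or complex staghorn stones | No |
| Exclusion 2: obvious surgical contraindications | Open-ended; examples are cardiopulmonary and coagulation problems |
| Exclusion 3: previous renal stone surgery, stent or nephrostomy in place | No |
| Exclusion 4: renal trauma, urinary malformation | No |
| Section 10 list of intraoperative events | Failure to reach lithotomy at the start is not listed |
| Section 16 allocation | No check of position mentioned |

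The gap is established by this reading. What follows only gauges its possible size.

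**2. The plan's own figure.** The 200 patients in section 14 rest on clinic and surgical volume. No event rate, effect or power is given, so there is nothing to reproduce, and no stated figure changes. At 1:1 there are about 100 per arm.

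**3. Controls affected.** Let f be the share of enrolled patients who cannot take lithotomy (assumption; the documents give none). Expected number among controls = 100f. Chance of at least one = 1 − (1 − f)^100.

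- f = 1%: 1 expected; chance 0.63
- f = 2%: 2 expected; chance 0.87
- f = 5%: 5 expected; chance 0.99
- f = 10%: 10 expected; chance above 0.99

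**4. Affected controls cross over and are analysed as randomised.** Assume complication rates of 30% (control) and 15% (experimental), 100 per arm, two-sided 5%. The observed control rate becomes (1 − f) × 0.30 + f × 0.15. Power = Φ{[d − 1.96 √(2p̄(1 − p̄)/100)] / √[(p₁(1 − p₁) + p₂(1 − p₂))/100]}, where p₁ and p₂ are the control and experimental rates, d their difference and p̄ their mean.

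- f = 0: 30.0% against 15%; power 72.2%
- f = 2%: 29.7%; power 70.7%
- f = 5%: 29.25%; power 68.2%
- f = 10%: 28.5%; power 64.0%

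This is dilution towards no difference, not imbalance between the arms.

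**5. Affected controls are dropped.** Assume no treatment effect, with a complication risk of 40% in affected patients and 15% in others. An arm that keeps its affected patients has rate (1 − f) × 0.15 + f × 0.40 = 0.15 + 0.25f. The control arm without them has 15.0%.

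- f = 2%: 15.5% against 15.0%, a gap of 0.5 points
- f = 5%: 16.25% against 15.0%, 1.25 points
- f = 10%: 17.5% against 15.0%, 2.5 points

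**6. Affected controls are counted by the operation received.** Under the same assumptions, the experimental group then holds 200f affected patients among 100 + 100f, a share of 2f/(1 + f). Its rate is 0.15 + 0.25 × 2f/(1 + f).

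- f = 2%: 0.15 + 0.25 × 4/102 = 16.0%, a gap of about 1.0 point
- f = 10%: 0.15 + 0.25 × 20/110 = 19.5%, a gap of about 4.5 points

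In steps 5 and 6 the gap runs against the experimental technique, because affected patients were assumed to be at higher risk. A lower risk would reverse it.

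**The case against.** The strongest reply is that the protocol may already cover the matter. The exclusion for obvious surgical contraindications is open-ended, and in a trial of two operations, inability to take the position that one of them needs could be read as a contraindication. The guideline cited in inclusion criterion 1 cannot be inspected here. Spinal and joint disease is usually evident before surgery, a single surgeon performs all the operations, and allocation in the operating room does not mean that suitability is first judged there. The background also concludes in favour of patients with some hydronephrosis and a small stone burden, not of those with positioning problems. All this makes it plausible that such patients would be screened out informally. It does not make the exclusion reliable: its examples point elsewhere, and the background treats the limitation as a situation favouring the experimental operation, not as a bar to surgery.

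A reader might infer that some control patients will certainly be unable to receive their operation. The documents do not support that. The background says often, not always; it is not an eligibility statement; and no frequency is given.

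A reader might also infer from section 8, which describes the groups by the operation that participants underwent, that a crossover would be counted as experimental. That is a possible reading only. Section 11 says surgery follows the randomisation, section 16 defines the groups by the number drawn, and an analysis plan that is not shown may settle the populations. Nor does the protocol say that these patients are dropped, since failure to reach lithotomy is not on the section 10 list. The claim that the comparison is biased whatever happens fails as well, because crossovers analysed as randomised only dilute it.

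Finally, the sizes are wholly assumed and modest. At a 15% rate with 100 per arm, the standard error of the difference is √(2 × 0.15 × 0.85/100) = 5.0 points, larger than any gap in steps 5 and 6. This stands, and it limits the severity.

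**Conclusion.** The point holds in conditional form. As written, the eligibility criteria allow randomisation of patients who may be unable to undergo the control operation, and the protocol does not say what happens to them. Eligibility belongs in the protocol, so an unseen analysis plan would not close this gap.

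The consequence depends on handling. Under analysis as randomised, with assumed rates of 30% and 15%, power falls from 72.2% to between 70.7% and 64.0% if 2% to 10% are affected. With control-only loss and assumed risks of 40% and 15%, the control rate falls by 0.5 to 2.5 points and the arms are no longer comparable. None of these inputs comes from the documents. Whether any such patient would be enrolled is unknown. Severity is low to moderate.

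**What to change.** Reconcile section 6 with sections 10 and 11. Add one eligibility line, checked and recorded before randomisation, that the participant is judged able to undergo either protocol procedure, including its positioning. Log candidates who do not meet it and keep them outside the randomised comparison; any who have the new operation can be described as a separate series. State that all randomised patients are analysed in their allocated group, and reword section 8 so that the groups are defined by allocation. How patients with positioning limits are managed clinically is for the investigators to decide.

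The cost is a pre-operative check and a few fewer eligible patients. Under the same assumed 2% to 10%, reaching 200 participants would need about 200/0.98 = 204 to 200/0.90 = 222 otherwise eligible candidates. The trial would give no randomised evidence in the excluded group, but this design cannot provide that anyway, since those patients cannot receive the control operation.

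### Section 10 drops randomised patients from the final analysis because of events during surgery or incomplete data, so the arms compared are no longer the randomised arms

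*Protocol*

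**What the plan says.** Section 6 gives the ureteral catheter two functions: artificial dilatation to guide the puncture, and "to prevent stones from falling into the ureter to form ureteral stone street". It then limits its expectation for the catheter-free method: "we believe that for patients with certain hydronephrosis and little stone burden, it is theoretically feasible to perform tubeless PCNL without reverse insertion". Section 7 sets out to study the safety and efficacy of the method and where it can be applied.

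Section 10 ends with a rule on what may happen once the operation is under way. It opens with "If the following variations occurred during the operation: puncture difficulties in the", is interrupted by a page break and a missing figure, and resumes with "lithotomy position and inverse insertion of ureteral catheter-guided puncture". It goes on to list pyonephrosis that needs nephrostomy, channel bleeding for which a nephrostomy tube is kept, larger residual stones for which a tube is kept until a second operation, and "a ureteral stone street that necessitated ureteroscopic lithotomy by changing to the lithotomy position". Incomplete postoperative data are added. Patients in any of these groups "will be recorded by the study recruitment flow chart, but not included in the final data analysis".

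Section 11 says that in the control arm "the ureteral catheter was inserted under transurethral ureteroscopy in the lithotomy position" as the first step. Section 12 makes postoperative complications the primary endpoint, with bleeding and stone street among the components, and lists stone clearance as a secondary endpoint. Section 14 plans 200 patients at 1:1. Section 16 places allocation in the operating room.

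**The concern.** The rule selects the analysis set on what happened after allocation. Randomisation makes the two arms comparable as allocated. It does not protect a comparison restricted to patients whose operation went as intended, because the operation is the thing being compared.

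The listed events are also close to what the trial measures. Bleeding and stone street are primary endpoint components when they occur after surgery, and residual stones bear on stone clearance. Puncture difficulty and stone street correspond to the two functions that section 6 assigns to the catheter left out of the experimental arm, so they are the failures most relevant to where the method applies.

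If patients with these events go on to have more complications than the rest, and are removed more often from the catheter-free arm, that arm will look safer than it was among the patients assigned to it. The flow chart would show that the events occurred, but the final analysis would not count those patients' complications.

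**Working it through.** **Timing.** Section 11 says surgery follows the randomisation, and the control procedure begins with catheter insertion. Allocation must therefore precede the puncture. Every intraoperative event in the section 10 list, and any gap in postoperative data, comes after it.

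**Which arm is affected.** The legible triggers name no arm. The puncture clause is broken in the source. If it means changing to the lithotomy position and catheter-guided puncture, a control patient already has the catheter, and this removal can occur only in the catheter-free arm.

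**The plan's own figure.** 200 / 2 = 100 per arm. Section 14 bases the 200 on clinic and surgical volume, with no event rate or effect size, so there is nothing further to reproduce.

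**Inputs for the size of the bias.** All but the first are assumptions, not figures from the documents.
- n = 100 per arm (section 14).
- The primary endpoint is scored as any complication, yes or no.
- p = 10–20%: the complication rate in the control arm and in catheter-free patients who are not removed.
- c = 2–10%: the share of the catheter-free arm removed.
- r = 30–50%: the complication rate among those removed.
- No removals in the control arm.

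**Formula.** The rate among all patients assigned to the catheter-free arm is c·r + (1 − c)·p. The section 10 analysis shows p. The understatement is the difference, c·(r − p).

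- p = 0.10, lowest: 0.02 × (0.30 − 0.10) = 0.004, or 0.4 points.
- p = 0.10, highest: 0.10 × (0.50 − 0.10) = 0.040, or 4.0 points (14% as assigned, shown as 10%).
- p = 0.20, lowest: 0.02 × (0.30 − 0.20) = 0.002, or 0.2 points.
- p = 0.20, highest: 0.10 × (0.50 − 0.20) = 0.030, or 3.0 points (23% as assigned, shown as 20%).

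**Yardstick.** The 95% half-width for the arm difference is 1.96 × √(2p(1 − p)/100).
- p = 0.10: 1.96 × √0.0018 = 8.3 points.
- p = 0.20: 1.96 × √0.0032 = 11.1 points.

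At its largest the bias is 4.0/8.3 = 0.48 of the half-width for p = 0.10 and 3.0/11.1 = 0.27 for p = 0.20.

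**Sensitivity to the assumptions.** If those removed have the same complication rate as the rest (r = p), the bias is zero. If both arms lose patients, the bias in the difference is c₁(r₁ − p) − c₀(r₀ − p), with 1 for the catheter-free arm and 0 for control. It can cancel or change sign.

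**The case against.** The strongest case on the other side has four parts.

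- **The size is assumed.** The documents give no conversion or complication rate, and even the largest bias above is less than half the half-width. This stands. The case rests on the rule, not on a demonstrated bias.
- **The claim that the loss falls on one arm only rests on damaged text.** This stands too. A reader might infer that the rule as a whole strips patients from the catheter-free arm only. The documents do not support that: bleeding, residual stones, pyonephrosis and stone street could lead to removal in either arm. The one-arm statement applies only to the puncture clause, and only on the reading given.
- **Section 10 concerns events during the operation, section 12 those after it.** A reader might infer that the stone-street trigger deletes primary endpoint events outright. It does not, at least not literally. It removes patients with the intraoperative form of the event, along with whatever complications they have later.
- **The excluded patients are disclosed in the flow chart.** That helps a reader count them, but leaves the comparison restricted to the others.

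Three wider inferences are also tempting. One is that the unadjusted tests in section 19 are at fault. They are valid under randomisation, and covariate adjustment or interaction terms may sit in an analysis plan not seen here. Another is that sections 6 and 10 contradict each other because no hydronephrosis criterion is set. Section 6 speaks of theoretical feasibility in a background paragraph, section 7 aims to explore where the method applies, and wider enrolment is consistent with that. A third is to count each conversion as a failure, which would give a much larger hidden difference; section 12 does not define conversion as a complication.

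None of this answers the main point. An unseen analysis plan might add detail, but the exclusion is fixed in the protocol itself.

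**Conclusion.** The concern holds for the section 10 exclusion rule. Followed as written, it replaces the randomised comparison with one selected on post-allocation events that bear on the trial's outcomes, and it can favour the catheter-free method. Under the assumptions above, the understatement of that arm's complication rate is 0.2–4.0 points, against sampling uncertainty of 8–11 points. That is modest, but it is systematic and would not average out with more patients. The direction is not certain: it depends on those removed having more complications and on more being lost from the catheter-free arm. The second condition is likely only if the puncture clause means conversion to the catheter technique. The change is worth making before analysis because it is cheap and the rule is explicit.

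**What to change.** Amend section 10 so that all randomised patients who undergo surgery, including those with any listed intraoperative event, stay in the primary analysis in their randomised arm, with outcomes collected as for everyone else. Incomplete postoperative data should not by itself remove a patient; the method for missing values can be left to the analysis plan. Restore the broken puncture clause so that its meaning is clear.

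Report the number and proportion with each listed event by arm, with exact 95% intervals. For example, 2 of 100 gives 0.2–7.0% and 10 of 100 gives 4.9–17.6%. Keep the analysis that excludes these patients only as supportive. Optionally, describe conversions by the baseline pelvic effusion width that section 18 already collects. With so few cases this would be descriptive only.

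The cost is a protocol amendment, outcome collection for converted cases, and possibly a less favourable estimate for the new method. No extra recruitment or baseline data are needed, and neither eligibility nor clinical management changes.

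### Section 10 drops randomised participants from the final analysis for intraoperative events or incomplete postoperative data, so the only planned comparison is of groups selected after allocation

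*Protocol*

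**What the plan says.** Section 10 begins with ordinary eligibility criteria and then adds a rule that applies once surgery has started: "If the following variations occurred during the operation: puncture difficulties in the" … "lithotomy position and inverse insertion of ureteral catheter-guided puncture". The puncture item is broken at that point in the available text, so its exact sense is uncertain. The list goes on to pyonephrosis needing nephrostomy, "channel bleeding that was required to maintain a nephrostomy tube, larger residual calculi that needed a nephrostomy tube for a secondary surgery", and "a ureteral stone street that necessitated ureteroscopic lithotomy by changing to the lithotomy position". The sentence closes with "Or incomplete postoperative clinical data will be recorded by the study recruitment flow chart, but not included in the final data analysis".

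Read alone, the closing clause names only incomplete data. The event list belongs to the same loosely built sentence, and no other reading gives that list a consequence.

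The sequence is fixed elsewhere. Section 11 says "According to the randomization, the same associate chief urologist performed tubeless PCNL" with or without the catheter. Section 16 places allocation in the operating room, and section 17 says that the person carrying out the intervention knows the arm. Section 12 makes postoperative complications the primary endpoint, with operation time, hospital stay, cost and stone clearance as secondary endpoints. Section 19 names tests and a significance level but no analysis set.

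**The concern.** Randomisation makes the arms comparable at the moment of allocation. A rule that then removes people according to how the allocated operation went gives up that protection. Any difference between the analysed groups may reflect the technique, or it may reflect who was left in.

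Three features make this more than a formality. The removals arise from the procedure being compared. Some depend on judgement without a stated threshold (what counts as a larger residual stone, when bleeding needs a tube), made by an operator who knows the arm. And every endpoint is affected, because a removed participant's later complications, operation time, stay, cost and clearance all leave the comparison. Section 7 sets out to learn about the safety and efficacy of the new method, and participants in whom the operation ran into trouble are informative about both.

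**Working it through.** **Timing.** Allocation (section 16) comes before surgery (section 11), and surgery comes before every listed event and before the postoperative data (section 10). All removals are therefore made after randomisation.

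**Is it offset elsewhere?** The visible text of sections 12 to 19 has no analysis of all randomised participants, no sensitivity analysis and no handling of missing data. The flow chart in section 13 is not shown. Section 10 says that removed cases are recorded there, but recording them does not return them to the comparison.

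**Figures available.** The protocol gives 200 participants at 1:1 (section 14), that is 100 per arm, based on patient volume. It gives no complication rate, removal rate or allowance for removals, so it has no figure to reproduce, and the inputs below are assumptions.

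**Bounds for the primary endpoint**, read as any listed complication. Let rE and rC be the shares removed in the no-catheter and catheter arms. Assume 15% complications among the retained in both arms, so the restricted analysis shows a difference of 0. Let the event rate among the removed be anything from 0 to 1 in each arm. The all-randomised difference (no catheter minus catheter) then lies between:

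- lower = (1 − rE) × 0.15 − [(1 − rC) × 0.15 + rC]
- upper = [(1 − rE) × 0.15 + rE] − (1 − rC) × 0.15
- width = rE + rC

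For 5% and 2%: lower = 0.1425 − 0.147 − 0.02 = −0.0245; upper = 0.1425 + 0.05 − 0.147 = +0.0455.

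For 15% and 5%: lower = 0.1275 − 0.1425 − 0.05 = −0.065; upper = 0.1275 + 0.15 − 0.1425 = +0.135.

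| Removed, no catheter / catheter | Lower (points) | Upper (points) | Width |
|---|---|---|---|
| 2% / 1% | −1.15 | +1.85 | 3 |
| 5% / 2% | −2.45 | +4.55 | 7 |
| 5% / 5% | −5.0 | +5.0 | 10 |
| 15% / 5% | −6.5 | +13.5 | 20 |

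Equal removal rates do not close the range, because the people removed may differ between arms.

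**When the bias is zero.** If the removed have the same event rate e in both arms, the difference is (rE − rC) × (e − 0.15). It is 0 when e = 0.15 or when rE = rC, and it changes sign if the removal rates are swapped.

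**Stone clearance.** Suppose clearance is judged on the allocated operation and is 90% among the retained (assumed). Counting a share r removed for residual stone as not cleared gives (1 − r) × 0.90: 88.2% at r = 2%, 85.5% at 5% and 81.0% at 10%. The restricted analysis would report 90% each time. The rule can only raise the reported rate within an arm; this does not settle the difference between arms.

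**The case against.** The best defence is that the rule is deliberate. Section 6 describes tubeless surgery as leaving no nephrostomy tube, and section 11 describes both operations as ending without visible residual stone or active bleeding. Three of the five listed events (pyonephrosis, channel bleeding, larger residual stone) involve a nephrostomy tube and can occur in either arm, so those participants did not complete a tubeless operation. The removals are prespecified and recorded, the objective is exploratory, and the eligibility limits (stones under 3.5 cm, no infectious or complex staghorn stones) may keep them few. All of this stands, and it justifies a per-protocol set as a secondary analysis. It does not justify that set as the only comparison, because whether the operation could be completed is itself a result of the operation allocated.

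A reader might infer more than the documents support:

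- **That the trial plans an as-treated analysis.** Section 8 says "The participants who underwent tubeless PCNL without reverse insertion of a ureteral catheter were selected as the experimental group" and describes the control arm in the same way. But section 16 forms the groups by odd and even random numbers, and section 11 has surgery follow the randomisation. Section 8 is loose wording to be tidied, not a second fault.
- **That the bias favours the no-catheter arm.** Section 6 says that the catheter is thought to guide puncture and prevent stone street, which makes more removals without it plausible. Section 6 also says that puncture depends less and less on artificial hydronephrosis, and the puncture item cannot be read in full.
- **That primary endpoint events are deleted directly.** The listed events are intraoperative and the endpoint is postoperative. Bleeding and stone street overlap in kind only.
- **That the bias is shown to exceed sampling error.** An assumed case with 15% and 2% removed, all with events, gives 27.75% against 16.70%, or +11.05 points. The 95% half-width at those rates with 100 per arm is 1.96 × √(0.2775 × 0.7225/100 + 0.1670 × 0.8330/100) = 11.4 points, which is larger.

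**Conclusion.** The point holds, with high confidence, for the section 10 rule. As written, the final analysis compares groups selected after allocation, and nothing in the visible text offsets this. Bias is possible for the primary and all secondary endpoints. Its size and direction cannot be derived from the protocol, and it could be zero. Without assumptions about the removed participants' events, the uncertainty from removal alone equals the two removal rates added: 7 points at 5% and 2%, 20 points at 15% and 5%. Where those bounds lie rests on the assumed 15% among the retained, and the removal rates are assumed too.

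The rule should be changed before analysis. No test in section 19 can bring back participants left out of the data set, and endpoint data never collected cannot be recreated. A separate SAP might add analyses, but the rule stands in the protocol and has to be changed there.

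**What to change.** 1. In section 10, replace the exclusion with: *The main analysis includes all randomised participants in the arm to which they were allocated; none is removed because of an intraoperative event, and endpoint and 1-month data are collected for them as for all others.*
2. Clarify section 8 to match section 16: the groups are as allocated.
3. Count residual stone needing a second operation as not cleared by the allocated operation.
4. Add a missing-data rule to section 19. Participants with partial data stay in each endpoint they have. For the primary endpoint, any observed complication is an event; a participant with none observed and a component missing is treated as missing, not as event-free. Report missing data by arm and reason. For event/no-event endpoints, add a best-case/worst-case sensitivity analysis over all randomised participants, with everything missing set to event in one arm and no event in the other, then the reverse. This also covers the upward tilt that arises because participants with partial data are classified only when they have had an event. For operation time, stay and cost, analyse the available data and give the number missing by arm.
5. Report the listed intraoperative events by arm.
6. Keep the section 10 set only as a secondary per-protocol analysis.

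The cost is rewording in sections 8 and 10, a short addition to section 19 and modest extra data collection, since recording removals in the flow chart does not show that their endpoint and 1-month data are collected. Reported complication and clearance rates may look less favourable. Only analysis and data collection change, not clinical management.
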